1.0 Background

Although active surveillance for very low-risk prostate cancer has become more prevalent, evidence for the importance of local therapy for patients with intermediate-, high-risk and even oligometastatic disease is growing (1,2). The pivotal role of androgen signaling in prostate cancer progression has long been recognized, and suppression of androgen receptor-mediated effects on prostate cancer remains a pillar of its clinical management. For high-risk, potentially lethal prostate cancers, radiation is the only local treatment modality which has level 1 evidence demonstrating improved survival when used in concert with androgen suppression (2,3). However, in spite of the value of this combined approach, these patients remain at risk of dying from prostate cancer. Local recurrence remains the predominant mode of treatment failure, and strategies to improve the therapeutic index of radiation based therapy of intermediate and high risk prostate cancer are critically needed (3,4).

While studying androgen receptor (AR) transcriptional signaling in prostate cancer, our group unexpectedly found that stimulating AR transcriptional programs in androgen-deprived prostate cancer cells using AR agonists such as testosterone and dihydrotestosterone (DHT) leads to production of numerous, transient DNA double strand breaks (DSB) that require DNA repair machinery for resolution ⁴⁻⁶. These double strand breaks were mediated by the class II topoisomerase TOP2B, which acted as a transcriptional co-activator with the androgen receptor. Although all of the mechanistic causes and roles of these DSB in AR signaling are still unclear and are the subject of intense ongoing research in the group, the finding that AR stimulation could lead to TOP2B mediated DSB was highly reproducible and robust and presented a potential Achilles Heel of AR signaling in prostate cancer cells. In preclinical studies, the DSB produced by treatment of cells with a pulse of DHT led to significant selective sensitization of AR-positive cells to treatment with ionizing radiation *in vitro* and *in vivo*⁶.

Unfortunately, although these preclinical studies appeared very promising, the prospect of overt AR stimulation, even transiently, in treatment of localized prostate cancer (where conventional androgen deprivation plus IR therapy can be curative in many cases) raised many concerns for further clinical translation given the dependence of prostate cancers on AR signaling; thus, alternative strategies to overt AR stimulation were considered.

In particular, we hypothesized that some AR antagonists may be able to partially stimulate the AR and induce TOP2B-mediated DSB without allowing activation of AR mediated growth stimulation and transcriptional programs. Remarkably, in new preliminary data, among a series of tested AR antagonists, hydroxy-flutamide (FLU) allowed nuclear translocation of AR, and stimulated genome wide TOP2B-mediated DSB. In fact, when exposed to 10 uM FLU, a clinically achievable concentration, androgen-deprived, AR-positive, prostate cancer cells accumulated DSB, measured by neutral comet assay, at levels equivalent to irradiating them with 0.5 to 2 Gy of ionizing radiation. The level of breaks was also equivalent to that achieved by saturating levels of the AR agonist DHT. Androgen-deprived PCa cell lines also displayed increased γH2A.x foci, a widely accepted biomarker of DSB. Interestingly, the second generation, highly potent AR antagonist enzalutamide did not induce DSB in prostate cancer cells. Immunofluorescent staining of the androgen receptor (AR) demonstrated robust nuclear translocation in androgen-deprived cells following exposure to a wide range of doses of FLU but not to Enzalutamide, providing some explanation of the differing DSB inducing ability of these AR antagonists (see **Fig 1** below).

[figure not shown]
[figure not shown]

[figure not shown]
Fig. 1 The AR antagonist FLU, but not Enzalutamide, allows nuclear localization of AR (left). Flutamide, like DHT, stimulates DSB in AR+ Pca cells *in vitro* (middle) and *in vivo* (right).

Moreover, RNAi-mediated knockdown of either AR- or topoisomerase 2 beta (TOP2B) prevented DSBs resulting from FLU exposure, which is consistent with mechanistic observations following stimulation with DHT⁶. Importantly, although LNCaP cells have a mutation in the AR increasing its activity, we also observed DSB formation in VCaP, CWR22Rv1, and LAPC4 cells as well, suggesting that PCa cells with wild-type AR will respond similarly. γH2AX foci increased over 6h exposure to DHT or FLU, yet this increase in γH2AX could be prevented by co-incubation with the antioxidant *N*-acetyl-*L*-cysteine (NAC, 5mM), suggesting that reactive oxygen species (ROS) contribute to the TOP2B-mediated DNA damage following AR signaling. To test the possibility that AR-mediated DSBs may radiosensitize AR-expressing PCa cells, DHT and AR-antagonists were used to induce DSBs in androgen-deprived LNCaP cells, followed by exposure to IR. Interestingly, a pulse of DHT or FLU significantly and synergistically enhanced the radiosensitivity of AR-positive VCaP prostate cancer cells (Fig 2A). Stimulation of castrated nude mice implanted with prostate cancer xenografts with a pulse of FLU followed by treatment with ionizing radiation also led to significant growth inhibition of the xenografts compared to mice treated with FLU alone or ionizing radiation alone, suggesting therapeutic benefit of the paradigm *in vivo* (Fig 2B).

Fig. 2. (A) Profound synergy of FLU plus IR in reducing clonogenic survival of VCaP cells *in vitro*. (B) Combination of a pulse of FLU followed by 6 Gy IR inhibits VCaP xenograft growth significantly greater than either agent alone.

Importantly, in these *in vivo* studies, immunohistochemical examination of biopsies from xenograft tissue displayed increased γH2AX foci, which increased from 0-12 hours and returned to basal levels by 24 hours. Similarly, AR was observed to be highly nuclear in localization under similar time-points (Fig 3).

These observations, if confirmed in humans, are potentially readily translatable to clinical practice. Such an effect would enhance the therapeutic index given its high specificity to AR-expressing tissues, and could be exploited on a repeated basis over a course of fractionated RT by dosing FLU at spaced intervals.

Fig. 3. AR in VCaP xenograft tissue biopsies following OH-Flu exposure in castrated setting

The primary goal of this study is to carry out a first-in-man pharmacodynamics clinical trial to test whether a pulse of FLU can induce DSB in men undergoing androgen suppression as part of their treatment strategy for localized prostate cancer.

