4.6 Data to be collected

The data that will be collected for this trial will be the results and/or findings of the procedures and assessments that are outlined in 4.5 and 4.6. Results/findings will also be abstracted from the source documents and records (e.g. clinic notes, radiology reports, lab reports, and recorded onto either study specific case report forms or within electronic database housed on the secure Radiation Oncology network drive. The data manager assigned to this trial will be responsible for the data collection with regard to clinical elements (PSA, etc.). The principal investigator or coinvestigators and/or assistants may also be responsible for collection and analysis of dosimetric and imaging data. Both data managers and/or investigators will have access to patient medical records and will record medical information from the medical record onto the relevant case report forms or database. The principal investigator will review the data on a quarterly basis for accuracy.

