5.1 Pre-implant Flutamide vs placebo dosing

Patients will receive either Flutamide single 250mg dose or placebo, taken orally 6-12 hours prior to the brachytherapy.

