5.2 Plasma, urine and serum sampling for analyses

5.2.1 Plasma assay for 2-hydroxyflutamide

2-hydroxyflutamide levels will be assayed both pre- and post-flutamide dosing in the initial non-randomized cohort. For the randomized cohort, only post-flutamide levels of 2-hydroxyflutamide will be assayed.

Blood samples (~4 ml) will be drawn into heparinized test tubes 0-10 days before drug administration (non-randomized initial cohort only), and also at 6-12 hours post-ingestion of Flutamide. Blood samples are to be immediately placed on ice after collection and centrifuged at 1300g for 10 minutes at 4 degrees C, and the plasma fraction to be separated and stored in polypropylene tubes at temp of -70 degrees C until analysis.

For analysis, specimens will be transferred to Analytical Pharmacology Core Laboratory and analyzed based on method described by Niopa et al.⁷

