6.2 Sample Size Justification and Accrual

This is a pilot trial, and will be utilized to design a larger study to establish measures for such parameters with a reasonable level of precision. We will enroll 30 patients onto the trial, with goal of at least 24 evaluable patients accrued.

In the run-in phase, a total of 6 evaluable patients will be accrued to receive Flutamide administration. We will use a Bayesian monitoring rule to determine if the study is feasible. Specifically, we would consider it is “infeasible” if the probability of not observing greater than or equal to 5% of prostate cancer cells having gammaH2AX foci is more than 50%. Based on the Bayesian monitoring rule in Section 6.3, if there is less than or equal to 1 out of 6 cases with detectable DNA double strand breaks (i.e., greater than or equal to 5% of prostate cancer cells having gammaH2AX foci on patient level), the study will be considered as infeasible and will not proceed into the randomization part.

If the study proceeds into the randomization part, a total of 18 evaluable patients will be randomized in a 2:1 ratio to either receive Flutamide (12 patients) or not (6 patients). A total of 18 patients treated with Flutamide (6 from run-in and 12 from randomization) will produce a two-sided 90% confidence interval with a width ranging from 0.35 to 0.42 (if the true proportion of prostate cancer cells having gammaH2AX foci is 30%-80%). A total of 6 patients in control will produce a two-sided 90% confidence interval with a width approximately less than 0.5 (if the true proportion of prostate cancer cells having gammaH2AX foci is less than 10%).

All eligible patients will be offered enrollment on the study, and we estimate a 20% dropout and nonevaluable rate. Patients who drop out prior to the biopsy/brachytherapy procedure will be replaced; patients who drop out after biopsy/brachytherapy will not be replaced. In order to ensure at least 24 evaluable patients are available, we plan to enroll ~30 patients onto this trial. Given the minimal addition to standard therapy and effort requirement from patient, we expect to accrue at least 2-3 patients/month, and the full accrual will be completed in 2 years.

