In male rats administered an oral 5 mg/kg dose of ¹⁴C-Flutamide neither Flutamide nor any of its metabolites is preferentially accumulated in any tissue except the prostate. Total drug levels were highest 6 hours after drug administration in all tissues. Levels declined at roughly similar rates to low levels at 18 hours. The major metabolite was present at higher concentrations than Flutamide in all tissues studied. Following a single 250 mg oral dose to normal adult volunteers, low plasma concentrations of Flutamide were detected. The plasma half-life for the alpha-hydroxylated metabolite of Flutamide is approximately 6 hours. Flutamide, *in vivo*, at steady-state plasma concentrations of 24 to 78 ng/mL, is 94% to 96% bound to plasma proteins. The active metabolite of Flutamide, *in vivo*, at steady-state plasma concentrations of 1556 to 2284 ng/mL, is 92% to 94% bound to plasma proteins. **Metabolism**

The composition of plasma radioactivity, following a single 200 mg oral dose of tritium-labeled Flutamide to normal adult volunteers, showed that Flutamide is rapidly and extensively metabolized, with Flutamide comprising only 2.5% of plasma radioactivity 1 hour after administration. At least six metabolites have been identified in plasma. The major plasma metabolite is a biologically active alphahydroxylated derivative which accounts for 23% of the plasma tritium 1 hour after drug administration.

The major urinary metabolite is 2-amino-5nitro-4-(trifluoromethyl)phenol.

Excretion

Flutamide and its metabolites are excreted mainly in the urine with only 4.2% of a single dose excreted in the feces over 72 hours.

Plasma Pharmacokinetics of Flutamide and HydroxyFlutamide in Geriatric Volunteers (mean \pm SD)

	Single Dose Flutamide	HydroxyFlutamide	Steady- State Flutamide	HydroxyFlutamide
Cmax (ng/mL)	25.2 \pm 34.2	894 \pm 406	113 \pm 213	1629 \pm 586
Elimination half-life (hr)	---	8.1 \pm 1.3	7.8	9.6 \pm 2.5
Tmax (hr)	1.9 \pm 0.7	2.7 \pm 1.0	1.3 \pm 0.7	1.9 \pm 0.6
Cmin (ng/mL)	---	---	---	673 \pm 316

Special Populations

Geriatric Following multiple oral dosing of 250 mg t.i.d. in normal geriatric volunteers, Flutamide and its active metabolite approached steady-state plasma levels (based on pharmacokinetic simulations) after the fourth Flutamide dose. The half-life of the active metabolite in geriatric volunteers after a single Flutamide dose is about 8 hours and at steady-state in 9.6 hours.

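### Does calling 10 µM hydroxyflutamide reachable in patients conflict with the protocol's own plasma data, and must Section 6 plan a summary of the plasma level?

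*Combined protocol and SAP*

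**What the plan says.** Section 1.0 (Background) uses FLU to mean hydroxyflutamide and states that, "when exposed to 10 uM FLU, a clinically achievable concentration, androgen-deprived, AR-positive, prostate cancer cells accumulated DSB". The sentence names no dosing regimen, no body fluid or tissue, and no reference. The same section gives the trial's aim as "to test whether a pulse of FLU can induce DSB in men undergoing androgen suppression".

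Section 5.1 sets the regimen: "Patients will receive either Flutamide single 250mg dose or placebo, taken orally 6-12 hours prior to the brachytherapy".

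Section 9.0 (Description of the Drug) tabulates hydroxyflutamide Cmax in geriatric volunteers as 894 ± 406 ng/mL after a single dose and 1,629 ± 586 ng/mL at steady state. Its Distribution paragraph adds that the active metabolite, "at steady-state plasma concentrations of 1556 to 2284 ng/mL, is 92% to 94% bound to plasma proteins".

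Section 5.2.1 has blood drawn before dosing in the run-in cohort "and also at 6-12 hours post-ingestion of Flutamide". It continues: "For the randomized cohort, only post-flutamide levels of 2-hydroxyflutamide will be assayed". Section 7.0 gives pharmacokinetics as the purpose of the pre-biopsy blood sample. Section 4.6 describes the trial data as "the results and/or findings of the procedures and assessments that are outlined in 4.5 and 4.6". Section 6 covers the γH2AX endpoint, the interval widths, accrual and the feasibility rule, and does not mention the plasma level. Section 6.2 says: "This is a pilot trial, and will be utilized to design a larger study".

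**The concern.** Two things catch the eye. First, a reader who has only the Background would expect patients to reach about 10 µM, whereas the protocol's own table puts the average peak after one dose at less than a third of that. If the preclinical case depended on that concentration, the rationale would be weaker than it reads.

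Second, the trial draws blood for the metabolite in both cohorts but plans no summary of it. The draw may fall anywhere in a six-hour window during which the level declines appreciably, so a level without its time since ingestion is hard to compare between patients. The protocol does not say in terms that the clock times of ingestion, draw and biopsy are recorded. For a pilot meant to inform a larger study, foci paired with level and hours since dose would be useful, and an ingestion time not noted on the day might be lost.

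**Working it through.** **Inputs.** Flutamide molecular weight 276.22 (Section 9.0). Hydroxyflutamide adds one oxygen: 276.22 + 16.00 = 292.22 g/mol (derived, not stated). Cmax means and SDs, the single-dose half-life of 8.1 ± 1.3 h and Tmax of 2.7 h come from the Section 9.0 table. The 6 h half-life in normal adults and the 1556–2284 ng/mL range come from the Distribution text. The table does not state its single dose; I take it as 250 mg.

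**Conversion.** µM = (ng/mL) / 292.22, so 10 µM = 2,922 ng/mL.

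| | Mean Cmax | Mean + 2 SD | 10 µM relative to mean |
|---|---|---|---|
| Single dose | 894/292.22 = 3.06 µM | (894 + 812)/292.22 = 5.84 µM | 3.3 times; (2,922 − 894)/406 = 5.0 SD above |
| Steady state | 1,629/292.22 = 5.57 µM | (1,629 + 1,172)/292.22 = 9.59 µM | 1.8 times; (2,922 − 1,629)/586 = 2.2 SD above |

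The separate steady-state range is 1556/292.22 = 5.3 µM to 2284/292.22 = 7.8 µM.

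**Share of peaks above 10 µM.** At steady state it is 1.4% if Cmax is normal and 3.2% if lognormal. After a single dose it is below 0.001% (normal) or 0.16% (lognormal). If the ends of the 1556–2284 range are treated as group means with the table's SD of 586 (an assumption), z = (2,922 − 1,556)/586 = 2.33 and (2,922 − 2,284)/586 = 1.09, which give about 1% and 14%. These shares are rough: the number of volunteers and the shape of the distribution are unknown.

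**Timing.** Assume mono-exponential decline from the peak: C(t) = Cmax × 0.5^((t − Tmax)/half-life).

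- At 6 h: 894 × 0.5^(3.3/8.1) = 894 × 0.754 = 674 ng/mL = 2.3 µM.
- At 12 h: 894 × 0.5^(9.3/8.1) = 894 × 0.451 = 403 ng/mL = 1.4 µM.
- Ratio C(12 h)/C(6 h) = 0.5^(6/half-life): 0.50, 0.60 and 0.64 for half-lives of 6, 8.1 and 9.4 h (8.1 + 1.3). That is a fall of 36–50% across the window.

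**What in the design uses a concentration?** The widths in Section 6.2 depend on 18 and 6 patients and on assumed proportions. The rule in Section 6.3 depends on a Beta(0.1, 0.9) prior, a 50% threshold and a 70% posterior probability. None of these takes a drug level as input. Even if preclinical optimism shaped the prior, it carries the weight of 0.1 + 0.9 = 1 patient, so the observed biopsies soon dominate it.

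**Are the times available?** The Section 4.5 calendar places study drug at 12 to 6 hours before the procedure and a hydroxyflutamide draw on the biopsy day. Sections 5.1 and 5.2.1 set 6–12 h windows, and compliance with them can be checked only if the times are known. Section 4.6 includes abstraction from source records, and Section 10.0 retains operative and laboratory records. Nothing in Section 4.6 excludes clock times.

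**The case for a change.** The best argument for acting is that the arithmetic is right and the remedy nearly free. By the protocol's own table, 10 µM is far out in the tail for a single dose. Section 1.0 also reports that xenograft foci rose over 12 hours and were back to baseline by 24, so the readout itself depends on time since dose. A line in Section 6 and three recorded times would need no extra blood, patient or alpha.

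The numerical contrast stands, and a citation or regimen beside the phrase would make the Background clearer. The rest carries less weight. Reachable does not mean typical, and the sentence makes no claim about one 250 mg dose. The rationale does not rest on 10 µM alone: Section 1.0 also reports AR nuclear translocation over a wide range of doses and foci in xenografts after a pulse. The plasma figures are totals, and Section 9.0 notes accumulation in the prostate (in rats, with no amount given), so they do not measure exposure in the tissue that is biopsied.

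A listing for at most 18 flutamide patients would support no inference, and the plasma level is not an objective in Section 2.0. In the double-blind part the level can reveal the arm, so it would in any case be set beside the foci only after scoring. The risk of a lost ingestion time is real but speculative, since the case report forms are not part of the document.

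**Conclusion.** No change to the plan follows. The Background phrase lacks a regimen and a source, and it sits well above the single-dose peak in Section 9.0 (10 against a mean of 3.1 µM) and near the upper tail at steady state (mean plus 2 SD 9.6 µM; other range 5.3–7.8 µM). That is a loose phrase about a cell experiment. It does not contradict the table, and it does not show that exposure in the trial is inadequate, because the lowest active concentration and human prostate levels are not given.

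The missing summary is a gap that analysts fill sensibly: a level collected for pharmacokinetics, in a stated time window, will be reported descriptively with time since dose. Writing this down would alter no estimate, interval, error rate or stopping boundary.

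The figures assume a molar mass of 292.22 for the metabolite, a 250 mg single dose in the table, geriatric volunteers as a fair guide to these patients, and simple exponential decline after the peak. With the parent drug's weight of 276.22 instead, the means become 3.2 and 5.9 µM and the steady-state mean plus 2 SD becomes 10.1 µM, which makes a conflict harder still to assert.

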2.0 Study Objectives

Primary objective:

To confirm DNA double strand breaks occur in prostate cancer tissue following pulse-dose Flutamide administration in patients who are androgen suppressed, as compared to control patients receiving placebo.

Exploratory objective:

To explore the feasibility of detecting cancer-specific alterations in DNA methylation and structure within urine and plasma, and the kinetics for these measures when compared with PSA values and clinical response. We will examine whether prostate cancer specific DNA methylation alterations at a panel of frequently hypermethylated loci (e.g. GSTP1, PTGS2, MDR1, APC, RARbeta, gene promoters) can be used as a DNA based biomarker for tracking therapeutic response.

3.0 Study Population

The target population will be patients with a diagnosis of adenocarcinoma of the prostate who are seen in consultation at the Department of Radiation Oncology and Molecular Radiation Sciences. Approximately 400 patients per year with the diagnosis of prostate cancer are seen in the Department of Radiation Oncology. Within this group of patients, approximately 50% are eligible for brachytherapy based on having intact prostate (not post-prostatectomy), gland size, relative absence of lower urinary tract obstructive symptoms, and no prior transurethral resection of prostate (TURP). Of this subset, approximately 60% will receive androgen suppression with brachytherapy due to intermediate- or high-risk disease. Approximately 80% of patients offered brachytherapy at consultation decide to receive their treatment at Johns Hopkins. Overall, we currently perform 4 brachytherapy procedures per month on average, for a yearly total of approximately 50 cases.

3.1 Eligibility criteria

3.1.1 Inclusion criteria

- Histologically confirmed, localized (M0) adenocarcinoma of the prostate
- Clinical stages T1c – T3b, Mx or M0
- At least one biopsy core with Gleason 7 or higher disease
- The patient has decided to undergo brachytherapy plus androgen suppression as treatment modality for his prostate cancer (with or without supplemental external beam radiation)
- Suitable volume of disease for biopsy, defined as one or more of the following:
 - MRI scan of the pelvis with ≥ 1 identifiable lesion as being PI-RADS 4 or 5, plus minimum of at least 0.5cm in any dimension

OR

- Clinically palpable disease corresponding to (ipsilateral to) any involved core on biopsy

- Signed study-specific consent form prior to registration

